7.4. Multicenter Studies

This study will be conducted by multiple investigators at multiple sites internationally. The countries will be categorized into geographic regions (US, EU, rest of world) which will be used for subgroup analyses, described in Section [7.14](#).

7.5. Multiple Comparisons/Multiplicity

No statistical tests will be performed.

7.6. Patient Disposition

The following patient disposition summaries will be provided (details of the analysis populations can be found in Section [7.1.1](#)):

- The total number and percentage of patients entering each statistical analysis population is defined in Section [7.1.1](#) (analysis population: all entered patients).
- The number and percentage of patients who entered the study, were treated, and screen failed will be provided overall and by screen fail reason (analysis population: all entered patients).
- The number and percentage of patients who were treated and completed treatment, and the number and percentage of patients who discontinued the treatment at any time, by primary reason for discontinuation of treatment (analysis population: safety population).

- The primary endpoint of Study KGAE is the proportion of patients discontinued from study treatment due to AEs through the last treatment visit.
- The number and percentage of patients who were treated and completed the study, and the number and percentage of patients who discontinued the study at any time, by primary reason for discontinuation (analysis population: safety population).

All patients who were treated (i.e., in the safety population) and discontinued from study treatment will be listed together with the discontinuation reason, and the timing of discontinuation from the study will be reported.

Patient allocation by region, country, and center/site will be summarized with the number of patients who entered the study, number of treated patients, number of patients discontinued from study treatment, and number of patients discontinued from the study.

7.7. Patient Characteristics

7.7.1. Demographics and Baseline Characteristics

Patient demographic variables and baseline characteristics will be summarized for the safety population. The continuous variables will be summarized using descriptive statistics (mean, median, standard deviation, and range [minimum and maximum]), and the categorical variables will be summarized using frequency counts and percentages.

The following demographic information will be included:

- age
- sex (male, female)
- race (American Indian or Alaska Native, Asian, Black or African American, Native Hawaiian or Other Pacific Islander, White, Multiple, Other, or Not Reported)
- ethnicity (Hispanic or Latino, Not Hispanic or Latino, Not reported, or Unknown)
- region (US, EU, or rest of world)
- country
- weight (kg)
- weight category (<60 kg, ≥60 to <100 kg, or ≥100 kg)
- height (cm)
- BMI (kg/m²), and
- BMI category (Underweight [<18.5 kg/m²], Normal [≥18.5 and <25 kg/m²], Overweight [≥25 and <30 kg/m²], Obese [≥30 and <40 kg/m²], or Extreme obese [≥40 kg/m²]).

By-patient listings of basic demographic information for the safety population will be provided.

The following baseline disease/clinical characteristics will be included:

- age at onset (years): calculated as the difference between date of onset of AD and the date of birth collected on the CRF
- duration since AD onset (years): calculated as the difference between date of informed consent and the date of onset of AD collected on the CRF
- duration since AD onset category (0 to <2 years, 2 to <5 years, 5 to <10 years, or ≥10 years)
- anatomical area affected by AD:
 - head
 - trunk (internal/medial axillae and groin)
 - upper extremities (includes external axillae)
 - lower extremities (includes buttocks and feet), and
 - at least 2 areas
- AD treatment used in the past:
 - none
 - topical corticosteroids, and
 - topical calcineurin inhibitors
 - systemic treatments: systemic corticosteroids, cyclosporine, mycophenolate-mofetil, IFN- γ , janus kinase inhibitors, azathioprine, methotrexate, phototherapy, photochemotherapy, dupilumab, tralokinumab, and other biologics (e.g., B-cell depleting biologics)
 - other non-biologic medication/treatment
- IGA score: 3 versus 4
- EASI score
- BSA
- PROMIS[®] anxiety score
- PROMIS depression score, and
- DLQI/CDLQI.

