4.1. Inclusion Criteria

Patients must meet all the following criteria to be eligible for this study:

1. Male or female adolescent (≥ 12 years to < 18 years and weighing ≥ 40 kg).
2. Chronic AD (according to American Academy of Dermatology Consensus Criteria) that has been present for ≥ 1 year before the screening visit (see [Appendix 2](#)).
3. Eczema Area and Severity Index (EASI) score ≥ 16 at the baseline visit.
4. Investigator Global Assessment (IGA) score ≥ 3 (scale of 0 to 4) at the baseline visit.
5. $\geq 10\%$ body surface area (BSA) of AD involvement at the baseline visit.
6. History of inadequate response to treatment with topical medications; or determination that topical treatments are otherwise medically inadvisable.
7. Apply a stable dose of non-medicated, non-prescription moisturizer at least twice daily for ≥ 7 days prior to the baseline visit.
8. Willing and able to comply with all clinic visits and study-related procedures and questionnaires.
9. For women of childbearing potential: agree to remain abstinent (refrain from heterosexual intercourse) or use a highly effective contraceptive method during the treatment period and for at least 18 weeks after the last dose of lebrikizumab.

NOTE: A woman of childbearing potential is defined as a postmenarcheal female, who has not reached a postmenopausal state (≥ 12 continuous months of amenorrhea with no identified cause other than menopause) and has not undergone surgical sterilization (removal of ovaries and/or uterus).

NOTE: The following are highly effective contraceptive methods: combined (estrogen and progestogen containing) hormonal contraception (oral, intravaginal, transdermal) associated with inhibition of ovulation, progestogen-only hormonal contraception (oral, injectable, implantable) associated with inhibition of ovulation, intrauterine device,

intrauterine hormone-releasing system, bilateral tubal occlusion, bilateral tubal ligation, vasectomized partner, or sexual abstinence. The reliability of sexual abstinence should be evaluated in relation to the duration of the clinical trial and the preferred and usual lifestyle of the patient. Periodic abstinence (e.g., calendar, ovulation, symptothermal, or postovulation methods) and withdrawal are not acceptable methods of contraception.

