7.1. Screening Visit (Day -30 to -7)

The purpose of the screening visit/period is to ensure that appropriate patients are entered into the study and that they remain stable during the pre-treatment period.

- Obtain written informed consent/assent prior to performing any study procedures
- Review Inclusion/Exclusion Criteria
- Complete medical history/review of systems
- Collect demographic information
- Measure vital signs
- Review immunization record
- Perform a complete physical examination, including height and weight
- Collect concomitant medication and procedure/therapy information
- Complete the following assessments: Investigator's Global Assessment (IGA), Body Surface Area (BSA), and Eczema Area and Severity Index (EASI)
- Draw blood samples for laboratory tests, including serum pregnancy
- Draw blood sample for hormone testing

- Collect urine sample for urinalysis
- Instruct the patient to apply a moisturizer at least twice daily

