7.13.4.1. Adolescent standardized Growth

Weight, height, and BMI data will be merged to the CDC standard growth data (released in 2000) by age and gender in order to compare patients' growth with the standard. Z-score and standardized percentile of weight, height, and BMI at each visit will be calculated and compared to the 2000 CDC growth charts. The summaries of growth data will be performed on the safety population.

The Z-score and percentile calculations are based on algorithms and data provided by the National Center for Health Statistics. The details are provided on the CDC website (CDC resources page [WWW]).

The following summaries and plots will be provided:

Table KGAE.7.7. Summary Table/Figure Related to Adolescent Standardized Growth

Summaries	Population
Summaries for baseline, mean change of actual measure, z-score and standardized percentile of weight, height, and BMI	Safety
Scatterplot of mean weight, height, and BMI standardized percentile versus lebrikizumab exposure time	Safety

Abbreviations: BMI = body mass index.

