7.14. Subgroup Analyses

7.14.1. Efficacy Subgroup Analyses

Subgroup analyses will be conducted for the secondary endpoints IGA (0,1) and EASI-75 across the treatment period in the safety population, using descriptive statistics.

The following subgroups will be analyzed:

- region (US, EU, or rest of world), and
- weight category (<60 kg, ≥60 to <100 kg, or ≥100 kg).

Some additional subgroup analyses may be added. The analysis of additional subgroups will not require an amendment to the SAP.

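### Baseline BMI categories use fixed limits with no age or sex term in a trial of patients aged 12 to under 18, although the SAP already plans BMI percentiles by age and gender

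*SAP*

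**What the plan says.** Protocol 4.1 sets the population: "Male or female adolescent (≥ 12 years to < 18 years and weighing ≥ 40 kg". No one is an adult at entry.

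SAP 7.7.1 lists the demographic variables for the safety population. One line reads: "BMI category (Underweight [<18.5 kg/m²], Normal [≥18.5 and <25 kg/m²", followed by Overweight from 25, Obese from 30 and Extreme obese from 40 kg/m². The line has no age or sex term. Nothing in 7.7.1 refers to percentiles or says that the categories serve only for comparison with other studies. The same list includes age, sex, height, weight, weight category and continuous BMI.

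SAP 7.13.4.1 treats BMI differently: "Weight, height, and BMI data will be merged to the CDC standard growth data (released in 2000) by age and gender". It continues: "Z-score and standardized percentile of weight, height, and BMI at each visit will be calculated and compared to the 2000 CDC growth charts". Table KGAE.7.7 there includes "Summaries for baseline, mean change of actual measure, z-score and standardized percentile of weight, height, and BMI", also on the safety population.

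**The concern.** The SAP handles BMI on two scales. In the growth section a BMI value is read against the patient's age and sex. In the baseline table the same value receives a verbal label whatever the age. Words such as Underweight and Normal carry a clinical meaning, and in a population made up only of adolescents an age-blind limit does not support that meaning. A 12-year-old and a 17-year-old of the same height and weight always get the same label.

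What is at stake is the description of who was studied: the reported shares of under- and overweight patients. No estimate of safety or efficacy is at stake.

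**Working it through.** The plan gives no figure to reproduce here. The sample-size text is redacted and has no bearing on a category definition. Three checks apply.

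**1. The sections side by side.**

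| Item | SAP 7.7.1 | SAP 7.13.4.1 |
|---|---|---|
| Scale | Fixed limits in kg/m² | z-score and percentile by age and gender |
| Baseline included | Yes | Yes |
| Counts per BMI category | Yes | Not specified |
| Population | Safety | Safety |

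The input for either scale is collected at screening (Protocol 7.1: "Perform a complete physical examination, including height and weight"). The only planned counts of under- and overweight patients are thus the age-blind ones.

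**2. Where the labels switch.** BMI = weight / height², so the height at which a limit L is crossed is √(weight / L). I start from the 40 kg entry minimum; the other weights are examples.

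- L = 18.5, 40 kg: √(40/18.5) = 1.470 m
- L = 18.5, 45 kg: √(45/18.5) = 1.560 m
- L = 18.5, 50 kg: √(50/18.5) = 1.644 m
- L = 25, 60 kg: √(60/25) = 1.549 m
- L = 25, 65 kg: √(65/25) = 1.612 m

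Above the first three heights a patient of that weight is labelled Underweight at any age. Above the last two, a patient of that weight falls short of the Overweight limit at any age. These heights show that the rule ignores age. They do not show that a given label is wrong: 40 kg at 170 cm is a BMI of 40/1.70² = 13.8, where Underweight may well be right.

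**3. An illustrative range.** To judge a label one needs age-specific reference values, which the documents do not give. Everything in this step is an assumption: log-normal BMI with median m and log-scale SD s; a healthy range from the 5th to the 85th percentile; overweight from the 85th percentile up. With F(x) = Φ(ln(x/m)/s):

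- share of the healthy group below 18.5 = (min[F(18.5), 0.85] − 0.05) / 0.80
- share of those above the 85th percentile who fall below 25 = max[0, F(25) − 0.85] / 0.15

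Example with m = 18, s = 0.16: F(18.5) = Φ(0.171) = 0.568, so (0.568 − 0.05)/0.80 = 65%. F(25) = Φ(2.053) = 0.980, so (0.980 − 0.85)/0.15 = 87%.

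Over s = 0.13 to 0.19:

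| Assumed median BMI | Healthy but below 18.5 | Above 85th percentile but below 25 |
|---|---|---|
| 17.5 to 19 (taken as younger) | 46–77% | 50–98% |
| 20 to 21 (taken as older) | 14–36% | 0–71% |

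The shares ignore the 40 kg entry minimum. That minimum removes the lightest patients, who are probably mostly the youngest, so it lowers the Underweight share. The table supports a direction (more mislabelling at younger ages, less at older ones) and not a number.

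**The case against.** The strongest reply is that the age- and sex-standardised information is already planned. Table KGAE.7.7 summarises baseline BMI percentile and z-score on the same population, and 7.7.1 also reports age, weight, height and continuous BMI. That stands, and it is why the point is minor. It does not remove the point, for two reasons. Table KGAE.7.7 specifies summaries and a plot of mean percentiles, not counts of patients per category. It also sits in SAP 7.13, which says that some of its displays may be left out of the study report. The baseline table could therefore appear without the growth table.

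Four stronger readings are tempting, and the documents do not support them.

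- *That BMI categories matter here because the dose is fixed.* Protocol 1.4 ties exposure to weight, not BMI. Weight is in the baseline table, and SAP 7.14.1 lists "weight category (<60 kg, ≥60 to <100 kg, or ≥100 kg" as an efficacy subgroup. BMI percentiles would not serve that purpose better.
- *That the two SAP sections contradict each other.* One follows growth over time and the other describes the population at baseline. They differ in convention, and both can be carried out as written.
- *That healthy adolescents will be called underweight, and overweight ones normal, in some known proportion.* The switching heights give no count of wrong labels, and the percentages above are assumptions. The SAP also does not itself describe its limits as adult ones.
- *That the percentiles are already programmed.* The SAP says only that they will be calculated.

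**Conclusion.** The point holds as a minor one. The fixed limits ignore the dependence of BMI on age and sex that the SAP recognises elsewhere, so the labels are not age-appropriate for this population and can misdescribe patients. That the youngest are most affected rests on the assumption that typical BMI rises through adolescence. The number affected cannot be derived from the documents.

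The reach is one row of one descriptive table. SAP 7.1.2 plans no inferential testing, no eligibility criterion uses BMI, and neither the primary endpoint nor any efficacy summary depends on it. BMI category is not among the listed subgroups, though SAP 7.14.1 allows others to be added without an amendment.

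**What to change.** In SAP 7.7.1, define the BMI categories from the baseline BMI-for-age-and-sex percentile planned in 7.13.4.1, and write the percentile limits for each category into the SAP. Bands such as below the 5th, 5th to below the 85th, 85th to below the 95th, and 95th or above are one possibility; they are not taken from the documents. Keep continuous BMI.

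If the fixed categories are to stay for comparison with other trials in the program, show them next to the percentile categories, label them as not age-adjusted, and refer to Table KGAE.7.7.

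No new data are needed. The cost is one more derived row if both are shown, or some loss of comparability with the other trials if the fixed categories are replaced.

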7.7.2. Medical History

Medical histories are defined as the conditions/events recorded on the *Medical History* eCRF with a start date prior to the first study drug injection. Notice if a medical history worsens in severity on or after the date of first injection, it will be recorded as an AE on the *Adverse Event* eCRF with the date of worsening as the start date.

The number and percentage of patients with medical histories will be summarized for the safety population using the MedDRA PT nested within SOC.

The number and percentage of patients with specific medical history events of interest prespecified on the *History Assessment* eCRF (hand dermatitis, facial dermatitis, conjunctivitis, herpes zoster, and others) will be summarized for the safety population.

7.8. Treatment Compliance

Treatment compliance with investigational product will be summarized for patients who receive at least 1 confirmed dose of lebrikizumab (i.e., the safety population). Treatment compliance for each patient will be calculated as:

$$\text{Treatment compliance (\%)} = 100 \times \frac{\text{Total number of injections administered}}{\text{Total number of injections expected}}$$

- The number of injections expected can be derived from the study drug dispense dataset.
- The total number of injections administered will be based on the *Study Drug Administration* eCRF page and on the prompt “Please select the number of syringes successfully injected” in the *Dosing Diary*.

A patient will be considered compliant if he or she received $\geq 75\%$ of the expected number of injections while enrolled in the study. Descriptive statistics for percent compliance will be summarized. Subintervals of interest, such as compliance between visits, may also be presented.

7.9. Prior and Concomitant Therapy

Medications will be classified into anatomical therapeutic chemical drug classes using the latest version of the WHO drug dictionary. Medication start and stop dates will be compared to the date of first dose of treatment to be classified as prior or concomitant.

Prior medications are those medications that start and stop prior to the date of first dose of study treatment. *Concomitant medications* are those medications that start before, on, or after the first day of study treatment and continue into the treatment period.

Prior medication and concomitant medication will be summarized by drug class and PT for the safety population.

Rescue medications used during the study treatment period will be presented for the safety population based on the information collected on the *Atopic Dermatitis Treatments* eCRF page. This will include: (1) topical therapy, (2) systemic therapy (e.g., systemic corticosteroids, phototherapy, cyclosporin, etc.). More information on the definition of rescue medications can be found in [Appendix 1](#).

7.10. Efficacy Analyses

[Table KGAE.7.3](#) includes the description and derivation of the efficacy measures and endpoints.

For categorical parameters, the number and percentage of patients in each category will be presented, as well as a 95% confidence interval for the percentage. The 95% confidence interval

will be constructed using the asymptotic method, without continuity correction (that is, the normal approximation to the binomial distribution). For continuous parameters, descriptive statistics will include n (number of patients), mean, standard deviation, median, minimum, and maximum. These summaries will be provided for the data as-observed, and after implementation of LOCF and MCMC-MI imputation methods.

The IGA, EASI, and BSA will be reported by clinic visit.

Table KGAE.7.3. Description and Derivation of Efficacy/Health Outcomes Measures and Endpoints

Measure	Description	Variable	Derivation/Comment	Imputation Approach if Missing Components
Investigator’s Global Assessment (IGA)	The IGA is a static assessment and rates the severity of a patient’s AD. The IGA is comprised of a 5-point scale ranging from 0 (clear) to 4 (severe), and a score is selected using descriptors that best describe the overall appearance of the lesions at a given time point.	IGA score	Single item. Range: 0-4 0 represents “clear” 4 represents “severe”	Single item, missing if missing
		
 IGA (0,1) with ≥2-point improvement^a IGA (0) 	
 Observed score of 0 or 1 and change from baseline ≤-2 Observed score of 0 	Missing if baseline or observed value is missing Single item, missing if missing
Eczema Area and Severity Index (EASI)	The EASI scoring system uses a defined process (Steps 1-5 below) to grade the severity of the signs of eczema and the extent affected. The extent of disease (percentage of skin affected: 0 = 0%; 1 = 1-9%; 2 = 10-29%; 3 = 30-49%; 4 = 50-69%; 5 = 70-89%; 6 = 90-100%) and the severity of 4 clinical signs (erythema, edema/papulation, excoriation, and lichenification) each on a scale of 0-3 (0 = none, absent; 1 = mild; 2 = moderate; 3 = severe) at 4 body sites (head and neck, trunk, upper limbs, and lower limbs). Half scores are allowed between severities 1, 2, and 3. Each body site will have a score that ranges from 0-72, and the final EASI score will be obtained by weight-averaging these 4 scores. Hence, the final EASI score will range from 0-72 for each time point.	EASI score	Derive EASI region score for each of head and neck, trunk, upper limbs, and lower limbs as follows: $EASI_{region} = (\text{erythema} + \text{edema/papulation} + \text{excoriation} + \text{lichenification}) * (\text{value from percentage involvement})$, where erythema, edema/papulation, excoriation, and lichenification are evaluated on a scale of 0 to 3, and value from percentage involvement is on a scale of 0 to 6. Then total EASI score is as follows: $EASI = 0.1 * EASI_{\text{head and neck}} + 0.3 * EASI_{\text{trunk}} + 0.2 * EASI_{\text{upper limbs}} + 0.4 * EASI_{\text{lower limbs}}$	NA: partial assessments cannot be saved.
		
 Change from baseline in EASI score Percent change from baseline EASI score^a 	Change from baseline: observed EASI score – baseline EASI score % change from baseline: $100 \times \frac{\text{Observed score} - \text{Baseline}}{\text{Baseline}}$	Missing if baseline or observed value is missing

		EASI-50 ^a	% improvement in EASI score from baseline $\geq 50\%$: % change from baseline ≤ -50	Missing if baseline or observed value is missing
		EASI-75 ^a	% improvement in EASI score from baseline $\geq 75\%$: % change from baseline ≤ -75	Missing if baseline or observed value is missing
		EASI-90 ^a	% improvement in EASI score from baseline $\geq 90\%$: % change from baseline ≤ -90	Missing if baseline or observed value is missing
Body Surface Area (BSA) Affected by AD	The BSA assessment estimates the extent of disease or skin involvement with respect to AD and is expressed as a percentage of total body surface. BSA will be determined by the investigator or designee using the patient palm = 1% rule.	BSA score	$BSA_{Total} = BSA_{head\ and\ neck} + BSA_{trunk} + BSA_{upper\ limbs} + BSA_{lower\ limbs}$	NA: partial assessments cannot be saved.
		Change from baseline in BSA score ^a	Change from baseline: observed BSA score - baseline BSA score	Missing if baseline or observed value is missing.
Dermatology Life Quality Index (DLQI)	The DLQI is a validated, dermatology-specific, patient-reported measure that evaluates a patient’s HRQoL. This questionnaire has 10 items that are grouped in 6 domains, including symptoms and feelings, daily activities, leisure, work and school, personal relationships, and treatment. The recall period of this scale is over the “last week”. Response categories and corresponding scores are: Very much = 3 A lot = 2 A little = 1 Not at all = 0	DLQI total score	A DLQI total score is calculated by summing all 10 question responses and has a range of 0-30 (less to more impairment) (Finlay and Khan 1994; Basra et al. 2008).	Score of 1 unanswered question = 0; If 2 or more questions are missing, the total score is missing. Note: #7B could be a valid missing while #7A is not “No.” That is, #7 should be considered as 1 question.
		DLQI (0,1) in patients who had baseline DLQI score >1	A DLQI (0,1) response is defined as a postbaseline DLQI total score of 0 or 1. A DLQI total score of 0-1 is considered as having no effect on a patient’s HRQoL (Khilji et al. 2002; Hongbo et al. 2005).	Missing if DLQI total score is missing
		4-point improvement in patients who had baseline DLQI score $\geq 4^a$	Change from baseline ≤ -4	Missing if baseline is missing or observed value is missing.

Not relevant = 0
 
Scores range from 0-30, with higher scores indicating greater impairment of QoL. A DLQI total score of 0-1 is considered as having no effect on a patient’s HRQoL (Hongbo et al. 2005), and a 4-point change from baseline is considered as the minimal clinically important difference threshold (Khilji et al. 2002; Basra et al. 2015).
	
DLQI total score change from baseline^a
	
Calculated as: observed DLQI (total score) - baseline DLQI (total score)
	
Missing if baseline or observed value is missing

	
DLQI symptoms and feelings domain
	
Sum of responses of questions 1 and 2: 1. How itchy, sore, painful or stinging has your skin been? 2. How embarrassed or self-conscious have you been because of your skin?
	
If 1 question in a domain is missing, that domain is missing.

	
DLQI daily activities domain
	
Sum of responses of questions 3 and 4: 3. How much has your skin interfered with you going shopping or looking after your home or garden? 4. How much has your skin influenced the clothes you wear?
	
If 1 question in a domain is missing, that domain is missing.

	
DLQI leisure domain
	
Sum of responses of questions 5 and 6: 5. How much has your skin affected any social or leisure activities? 6. How much has your skin make it difficult for you to do any sport?
	
If 1 question in a domain is missing, that domain is missing.

	
DLQI work and school domain
	
Sum of responses of questions 7A and 7B:
	
If the answer to question 7A is missing, this domain is

			7A. Has your skin prevented you from working or studying? 7B. If No: how much has your skin been a problem at work or studying?	missing. If 7A is No, and 7B is missing, this domain is missing.
		DLQI personal relationships domain	Sum of responses of questions 8 and 9: 8. How much has your skin created problems with your partner or any of your close friends or relatives? 9. How much has your skin caused any sexual difficulties?	If 1 question in a domain is missing, that domain is missing.
		DLQI treatment domain	Response of question 10: 10. How much of a problem has the treatment for your skin been, for example by making your home messy, or by taking up time?	If 1 question in a domain is missing, that domain is missing.
Children’s Dermatology Life Quality Index (CDLQI)	The CDLQI is designed to measure the impact of any skin disease on the lives of children. Patients ≤16 years will complete the CDLQI and should continue to complete the CDLQI for the duration of the study. The scoring of each question is: 
 • Very much = 3 • Quite a lot = 2 • Only a little = 1 • Not at all = 0 • Question unanswered = 0 • Question 7: 'Prevented school' (text-only questionnaire) = 3 	CDLQI total score	A CDLQI total score is calculated by summing all 10 question responses and has a range of 0-30 (less to more impairment) (Waters A et al. 2010).	Score of 1 unanswered question = 0; If 2 or more questions are missing, the total score is missing.
		CDLQI (0,1) in patients who had baseline CDLQI score >1	A CDLQI (0,1) response is defined as a postbaseline CDLQI total score of 0 or 1.	Missing if CLQI total score is missing
		CDLQI total score change from baseline ^a	Calculated as: observed CDLQI (total score) - baseline CDLQI (total score)	Missing if baseline or observed value is missing
		CDLQI symptoms and feelings domain	Sum of responses of questions 1 and 2: 1. Over the last week, how itchy, “scratchy”, sore or painful has your skin been? 2. Over the last week, how embarrassed or self conscious, upset or sad have you been because of your skin?	If 1 question in a domain is missing, that domain is missing.
		CDLQI sleep domain	Response of question 9 9. Over the last week, how much has	Single item, missing if missing

			your sleep been affected by your skin problem?	
		CDLQI leisure domain	
Sum of responses of questions 4, 5, and 6:
 
4. Over the last week, how much have you changed or worn different or special clothes/shoes because of your skin?
 
5. Over the last week, how much has your skin trouble affected going out, playing, or doing hobbies?
 
6. Over the last week, how much have you avoided swimming or other sports because of your skin trouble?
	If 1 question in a domain is missing, that domain is missing.
		CDLQI school or holiday domain	
Responses of questions 7:
 
If select 'Prevented school', score = 3
 
Last week,  If school time: was it school time? Over the last week, how much did your skin affect your school work?
 
OR
 
was it  If holiday time: holiday time? How much over the last week, has your skin problem interfered with your enjoyment of the holiday?
	Single item, missing if missing

		CDLQI personal relationships domain	Sum of responses of questions 3 and 8: 3. Over the last week, how much has your skin affected your friendships ? 8. Over the last week, how much trouble have you had because of your skin with other people calling you names, teasing, bullying, asking questions or avoiding you?	If 1 question in a domain is missing, that domain is missing.
		CDLQI treatment domain	Response of question 10: 10. How much of a problem has the treatment for your skin been?	Single item, missing if missing.
Patient-Reported Outcomes Measurement Information System (PROMIS®)	PROMIS is a set of person-centered measures that evaluate and monitor physical, mental, and social health in adults and children. There are PROMIS instruments for assessing anxiety and for assessing depression. Patients will complete pediatric versions of these for the duration of the study.	PROMIS anxiety total score ^a PROMIS depression total score ^a	A PROMIS anxiety has 8 questions on Emotion Distress-Anxiety (or Pediatric Anxiety) (Short Form 8a). Each score ranges from 1-5. Total raw scores are converted to T-scores, with higher scores representing greater anxiety. A PROMIS depression has 8 questions on Emotion Distress-Depression (or Pediatric Depressive Symptom) (Short Form 8a). Each score ranges 1-5. Total raw scores are converted to T-scores with higher scores representing greater depression. Calculation is made by HealthMeasures Scoring Service, powered by Assessment Center SM .	Total score can be derived even with partial response, as the instrument uses item-response theory method.
		Change from baseline in PROMIS anxiety total score Change from baseline in PROMIS depression total score	Change from baseline: observed score - baseline PROMIS anxiety total score Change from baseline: observed score - baseline PROMIS depression total score	Missing if baseline or observed value is missing

Abbreviations: AD = atopic dermatitis; HRQoL = health-related quality of life; NA = not applicable; QoL = quality of life.

^a Secondary endpoints.

